**Analytic Plan.** The proposed project is a cluster-randomized controlled trial (J=22 schools; 11 per treatment arm) comparing the efficacy of Wellness vs. Partnership services. As a general analytic plan, we will use hierarchical linear modeling (HLM) to evaluate the project aims. Specifically, we will use two-level HLM models to account for students being nested within schools. Though one might conceptualize this proposal as a three-level model (i.e., students nested within schools, and schools nested within sites), it would be neither feasible nor recommended to model site as a multilevel variable given there are only two sites in the design (56). In line with best practice, we will integrate site (i.e., SC vs. MD) as a covariate in the statistical models to contain any potential effects of this variable. Based on prior research conducted by the team, we expect intraclass correlations (ICCs) to warrant the incorporation of random intercepts to account for violations of independence. We will also test independence assumptions for the treatment parameters to determine how sensitive treatment effects are to potential violations of independence, and will include random slopes to account for nested treatment effects if ICCs exceed .01. For transparency, we will report both fixed and random effects (i.e. intercepts and slopes) of the model. Additionally, we will iteratively subset the model using a k-1 sensitivity analysis to determine the influence of individual sites on parameter estimates. We will estimate statistical models using full information maximum likelihood to accommodate any missing data (57). We will use maximum likelihood with robust standard errors to estimate models that include the Zero Inflated Poisson link function for count

PRINCIPAL INVESTIGATOR: [name]

outcomes (e.g. absences, referrals). This general analytic framework will be used in aims 1 and 2. Details, exceptions, and modifications to it are discussed below.

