Given the experiment will examine intent-to-treat effects in a real-world setting, we will conduct analyses to investigate variability in implementation and compliance to enhance causal effect interpretation of clients "as treated." Specifically, we will use a Bayesian Additive Regression Tree approach (BART; 61) to delineate the impact of key treatment assumptions (e.g., compliance, fidelity, etc.), as well as to estimate the impact of assumption violations on the estimation of causal effects in the design. BART is an extension of Classification and Regression Tree (CART) models that is based on a recursive partitioning algorithm that explains variation in the outcome through repeated splits of the data into homogenous subgroups that are similar on predictor variables. One significant strength of BART is that it is capable of handling a large number of predictors and incorporates higher-order interactions that may be excluded from parametric analysis. Research indicates that BART is insensitive to tuning parameters and produces more accurate estimates of treatment effects compared to other methods of analyzing treatment effect heterogeneity (i.e., propensity score matching, propensity-weighted estimators, instrumental variable procedures, and regression adjustment; 61). Note that this BART enhancement to the randomized, experimental design should not be mistaken for a Bayesian trial design.

*Power considerations.* The design originally included a planned sample size of approximately N=2800 (1400 per arm) for Aims 1 and 2. We previously revised power estimates for these study aims that consider the possibility of reduced participant involvement given COVID-19 and recruitment challenges more broadly, with a revised sample size of approximately N=1400 (700 per arm). With the research study period concluding in June 2023, we have revised the enrollment projection to a conservative estimate of N=1225. With our currently active sites (J=22) and the total number of students enrolled in the study (N=1225, including expected spring 2023 enrollment), assuming 30% of variance

PRINCIPAL INVESTIGATOR: [name]

explained in the primary outcomes by pre-test covariates, and 80% power, we have a minimum detectable effect size (MDES) of .29. If we reach our goal of 1400 students, we will be at .28.

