Estimating dose-response effects using a conventional, frequentist treatment\*dosage interaction would violate the strong ignorability assumption, confound effects with varying characteristics of participants and sites, and yield biased estimates (e.g., 69,70). The BART models proposed in the current application have demonstrated efficacy in estimating treatment effects in quasi-experimental studies that may vary as a function of a continuous variable, such as treatment dose (71). The BART approach will provide an estimate of the treatment effect for those who received the intervention conditional on baseline covariates (i.e., conditional treatment effect on treated). We will calculate conditional treatment effects on treatment for each individual following the Neyman-Rubin causal model (72,73). The BART models will yield an effect size for each varying level of exposure, as well as provide a credible interval (analogous to a frequentist confidence interval) for the effect estimate. The BART models will also allow missing data to be included as a feature in the predictive model using a "missingness incorporated in attributes" approach. This means that BART will use all available data. Kapleiner and Bleich (74) demonstrated that this approach is computationally efficient and that results are comparable to other advanced missing data approaches (e.g., multiple imputation).

We will conduct additional analyses to ensure the results from our original models are not due to random noise in the sample. Specifically, we will conduct 250 Monte Carlo simulations in which a random binomial variable will be generated to represent an instrumental variable such that it will be uncorrelated with covariates or outcomes. Then we will regress each of the outcomes on the binomial variable yielding a parameter representing the relationship between the instrumental and binomial variable that is unrelated to the outcomes. This analysis will test the sensitivity of our BART models on estimated treatment effects and determine how robust our credible intervals are.

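### The BART as-treated and dose-response models name no school-level term, and they rest on the same untested dose-ignorability assumption that the plan holds against the treatment-by-dosage interaction

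*Combined protocol and SAP*

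**What the plan says.** The Analytic Plan describes a "cluster-randomized controlled trial (J=22 schools; 11 per treatment arm"). For the general framework it says "we will use two-level HLM models to account for students being nested within schools", and it expects ICCs large enough to need random intercepts. Site enters as a covariate.

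For variation in compliance and fidelity, the section on Tier 3 model modifications says "we will use a Bayesian Additive Regression Tree approach". It describes BART as repeated splits of the data on predictor variables. Under Power considerations, the BART effect is conditional on baseline covariates, and "The BART models will yield an effect size for each varying level of exposure, as well as provide a credible interval". Neither place mentions a school term, a random intercept or a cluster-level variance, and no list of BART predictors is given.

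On dose, Power considerations says that a conventional treatment-by-dosage interaction "would violate the strong ignorability assumption, confound effects with varying characteristics of participants and sites, and yield biased estimates", and it turns to BART instead. The only robustness check described is 250 simulations of a random binomial variable constructed to be unrelated to covariates and outcomes. The Tier 3 section, however, makes the interaction of treatment with weeks of treatment its stated model.

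**The concern.** There are two separate problems.

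**Clustering.** Arm is constant within school, so the between-arm contrast has only 22 independent units behind it. A BART model with no school component treats about 1,225 students as independent for that contrast. Ordinary differences between schools can then look like an effect. Power considerations gives no power figure for dose-response because the method is Bayesian, so the credible interval is the only statement of precision for these results.

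**Ignorability.** BART relaxes the functional form. It does not remove confounding by variables that are not in the model. Weeks of treatment is determined after randomisation, and the plan expects Partnership to change it: the Conceptual Framework predicts a higher dose and the Outcomes section a longer service duration. Conditioning on baseline covariates does not by itself make such a dose ignorable. A dose curve could therefore be read as causal without the protection of randomisation.

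**Working it through.** **Inputs from the documents.** J = 22 schools, 11 per arm; "N=1225, including expected spring 2023 enrollment"; "assuming 30% of variance" "explained in the primary outcomes by pre-test covariates, and 80% power"; MDES .29, or .28 at N = 1400. Mean cluster size m = 1225/22 = 55.7. Not stated: the ICC, alpha and sidedness, and the level at which the 30% applies. I assume two-sided .05.

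**The plan's own figure.** MDES = M × √[4·ICC·(1−R²₂)/J + 4·(1−ICC)·(1−R²₁)/N], with M = 2.086 + 0.860 = 2.946 (t, 20 df).

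- With no clustering and normal multipliers: 2.802 × √(4/1225) = 0.160, or 0.160 × √0.70 = 0.134 with R² = .30. So .29 already assumes substantial clustering.
- It cannot be reproduced directly without an ICC. Back-solving gives ICC .059 with R² at both levels: 2.946 × √(0.00751 + 0.00215) = 0.290. It gives about .05 with R² at school level only, .041 at student level only, and .067 with normal multipliers and R² at both levels. A one-sided test would give .082.
- The .28 at N = 1400 is consistent within rounding.

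The plan's figure therefore implies an ICC of about .04 to .07 (two-sided).

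**Between-arm interval if school is ignored.** Design effect DE = 1 + (m−1)·ICC = 1 + 54.7·ICC. Relative width = 1/√DE. Coverage = 2Φ(1.96/√DE) − 1.

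| ICC (assumed) | DE | Relative width | Coverage |
|---|---|---|---|
| .01 | 1.55 | 0.80 | 88% |
| .02 | 2.09 | 0.69 | 82% |
| .04 | 3.19 | 0.56 | 73% |
| .06 | 4.28 | 0.48 | 66% |
| .10 | 6.47 | 0.39 | 56% |

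**Check with BART itself.** This used 200 simulated trials with 22 schools, 1,225 students, a covariate explaining 30% of variance, a true arm effect of 0, and between-school variance .041 against within-school variance .67, so residual ICC = .041/.711 = .058. The model had 40 trees; these settings are assumptions of this review.

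- No school term: mean 95% interval width 0.185, coverage 65%.
- School random intercept: width 0.389, coverage 92%.

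The width ratio is 0.185/0.389 = 0.48, in line with the formula.

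**Dose slope.** Weeks of treatment vary within schools, so the table does not apply to it. The approximate SE understatement is √[1 + (m−1)·ICC·ICC_dose]. At ICC .05 it is √(1 + 54.7 × .05 × .1) = 1.13 for a dose ICC of .1, and √(1 + 54.7 × .05 × .5) = 1.54 for a dose ICC of .5.

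**Ignorability.** In the same simulation the true dose effect was 0. An unmeasured severity variable had an assumed loading of 0.5 on dose and 0.25 on outcome; dose also had a loading of 0.3 on the pre-test and noise SD 0.8. The bias per unit of dose is 0.25 × 0.5/(0.5² + 0.8²) = 0.25 × 0.562 = 0.140. The dose SD is √(0.25 + 0.09 + 0.64) = 0.99, so the expected bias from −1 SD to +1 SD is 2 × 0.99 × 0.140 = 0.28. BART with a school intercept estimated 0.28 SD, and its 95% interval covered 0 in 16% of runs. A school term does not cure this.

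**The planned check.** A confounder of dose is related to both dose and outcome. The 250 simulated variables are built to be unrelated to outcomes and covariates, so they cannot reveal one. As described, they are not drawn by school either, so they do not test clustering.

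**The case against.** - **The plan is silent on school; it does not exclude it.** A reader might infer that BART is specified with independent errors. The documents do not say so, and the Analytic Plan says its general framework serves Aims 1 and 2, with exceptions and modifications to follow. This stands. Even so, nothing carries the random intercept into BART, whereas the subgroup analyses are explicitly placed in the two-level framework.
- **The ICC is unknown and could be small.** Tier 3 outcomes are difference scores, which cancel stable school differences, and BART conditions on covariates. This stands as a reason to show a range. At ICC .01 the interval is about 20% too narrow.
- **The coverage figures belong to the between-arm contrast.** This stands. They should not be read as describing a dose curve that varies mainly within schools.
- **No sentence claims that BART escapes ignorability.** Correct. A reader would infer it from the contrast drawn with the interaction. What the text does is raise the assumption against one method and leave it unmentioned for the other.
- **These analyses are secondary and partly labelled.** The Analytic Plan calls its dose-response work on The Guide quasi-experimental and additional to primary ITT, and BART is introduced for as-treated effects. This stands and limits the consequence, although causal language remains in the BART text.

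**Conclusion.** The point holds in this form: the BART text leaves school unaddressed, and dose ignorability is an unstated and untested assumption. If BART is run as described, between-arm intervals at a given exposure would be about 0.80 to 0.39 of the proper width over ICCs of .01 to .10. At the ICC of about .04 to .07 that MDES .29 implies, they would be roughly half the proper width. These sizes rest on an assumed ICC, two-sided .05 and equal school sizes. The 0.28 SD dose bias is an illustration under chosen loadings, not a forecast.

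Two stronger readings are not supported. The documents do not show that the intervals will be wrong, because a school term may be intended. The primary ITT inference is not affected, because it uses two-level models and no decision rule is tied to the BART intervals.

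The conflict over the treatment-by-weeks interaction needs no assumption: the Tier 3 section specifies it and Power considerations calls such an estimate biased.

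**What to change.** 1. State that every BART model accounts for school, for example through a school random intercept with site as a covariate as in the main models, and that the reported intervals come from that model. School as an ordinary splitting variable is not enough, because arm is constant within school. List the BART predictors and report the ICC.
2. State ignorability of dose given the listed covariates as an assumption. Report dose-response and as-treated results as observational and supplementary to ITT.
3. Add a sensitivity analysis for an unmeasured confounder of dose, alongside or instead of the noise-variable check.
4. Reconcile the Tier 3 interaction model with the criticism of it under Power considerations, and say which analysis gives the dose result.

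The cost is revised wording and a modest amount of extra analysis, including a check that the cluster-aware version keeps the planned handling of missing data within the trees. The price in results is wider intervals and a weaker causal claim.

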**D. Study Design/Approach.** The study will involve 22 middle schools (12 in SC, 10 in MD) in a cluster-RCT, with all schools receiving the Wellness intervention and half of the schools (6 in SC, 5 in MD) randomized to receive enhanced intervention including the two SEs (Partnership). Stratified random assignment of schools to the Wellness Group or the Partnership Group will be conducted. We will then use validated procedures (23, 24) to further stratify schools within each state. We will construct a composite inflate-suppress score derived from school data on rurality, average number of students per grade, percent white, percent receiving free/assisted lunch, and average school test performance. Rurality within the two study sites will be operationalized by using a federally developed classification system used by The US Census Bureau (i.e., a 9-point, "Rural-Urban Continuum"). The coding scheme will distinguish three metro county categories based on population size, and six non-metro county categories based on degree of urbanization, as well as adjacency to other areas and metro proximity. Per operationalization of rurality in the federally-based coding continuum, we can confirm that the SC study sites contain county classifications of rural and suburban, while the MD site is exclusively urban. We will separate this composite into three strata and randomly assign schools from these strata to receive either the Wellness Group or the Partnership Group.

In the 5-year longitudinal design, Year 1 will involve administrative start up, collection of pre-assessments and intervention launch; Years 1-4 will involve intervention versus comparison while participants are in 6th through 8th grades. Year 5 will involve analyses and dissemination. A comprehensive implementation manual will guide the study and will be updated and improved regularly through active guidance of a Stakeholder Advisory Board (SAB, see Tables 3 and 4 in Appendix). The SAB will provide significant input as this manual is developed during the study start-up period from January through July, 2019, and progressively improved through study duration (see Gantt chart in Figure 1 of the Appendix for a review of all study activities in time).

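### The 250-run Monte Carlo step, as described, cannot show that the BART effects or their credible intervals are robust

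*Combined protocol and SAP*

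**What the plan says.** The step closes the account of BART under Power considerations (Analytic Plan). Its purpose is given first: "We will conduct additional analyses to ensure the results from our original models are not due to random noise in the sample". The procedure follows: "we will conduct 250 Monte Carlo simulations in which a random binomial variable will be generated to represent an instrumental variable", constructed "such that it will be uncorrelated with covariates or outcomes". The fitting step is: "Then we will regress each of the outcomes on the binomial variable". The paragraph ends with the claim "This analysis will test the sensitivity of our BART models on estimated treatment effects and determine how robust our credible intervals are".

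The text does not say whether the variable is drawn per student or per school. It describes no refit of BART with the random variable, no school term in the regression, and no result that would count as passing or failing. One clause says the regression yields a parameter linking the instrument and the binomial variable, although the binomial variable is itself the stand-in for the instrument.

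Treatment was assigned to schools. Section D, Study Design/Approach, states "Stratified random assignment of schools to the Wellness Group or the Partnership Group will be conducted", within state and then within strata of a composite score. The Analytic Plan describes a "cluster-randomized controlled trial (J=22 schools; 11 per treatment arm". The planning sample is "N=1225, including expected spring 2023 enrollment". Dose, under the Tier 3 model modifications, is each student's weeks of treatment.

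**The concern.** Three things do not fit together.

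- **The model in the loop is not the model under test.** A regression of outcomes on a random variable says nothing about how BART estimates move or whether BART intervals cover.
- **The variable is not an instrument.** An instrument must affect treatment or dose, and no such link is described. A variable made unrelated to covariates and outcomes is a placebo.
- **The placebo may have the wrong unit.** Chance imbalance in this trial arises between two sets of 11 schools. If the placebo varies between students, school-level variation averages out of it and its spread is too narrow.

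At stake is the assurance in the stated purpose. If the observed arm effect were set against a student-level placebo spread, ordinary differences between schools could pass for signal. The check would also be silent on confounding of dose, which the same section gives as its reason for avoiding a conventional treatment-by-dose interaction.

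**Working it through.** **Inputs.** J = 22 schools, 11 per arm, and N = 1225, so n = 1225/22 = 55.68 per school (Analytic Plan and Power considerations). The number of draws is 250. The outcome SD is set to 1. The documents give no ICC, so .02, .057 and .10 are assumptions used as a range. Two-sided alpha of .05 is also assumed.

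**Calibration.** The Monte Carlo step has no stated figure to reproduce. The nearest is the minimum detectable effect size (MDES), .29 at N = 1225 and .28 at N = 1400, with 30% of variance explained and 80% power. The formula is

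MDES = (t[.975] + t[.80]) × sqrt{ICC(1−R²b)/(P(1−P)J) + (1−ICC)(1−R²w)/(P(1−P)Jn)}.

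With P = .5, an assumed ICC of .05, the 30% placed at school level and one school-level covariate (19 df), this gives .287 and .281, matching both figures. Solving for an MDES of .29 gives an ICC of about .041, .052 or .059, depending on whether the 30% sits at student level, school level or both. The assumed range therefore brackets what the plan's own figure implies.

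**Placebo spread, student-level draw.** SD = 2/sqrt(N) = 2/sqrt(1225) = .057. The ICC does not enter.

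**Null spread, school-level contrast (unstratified 11 v 11).** SD = sqrt{(4/22)(ICC + (1−ICC)/55.68)}.

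| Assumed ICC | Calculation | School-level SD | .0571 / SD |
|---|---|---|---|
| .02 | sqrt(.1818 × .0376) | .083 | 69% |
| .057 | sqrt(.1818 × .0739) | .116 | 49% |
| .10 | sqrt(.1818 × .1162) | .145 | 39% |

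**Allowance for stratification.** Strata or covariates that explain school differences would narrow the right benchmark. As a gauge only, remove 30% of the between-school variance by replacing ICC with .7 × ICC in the first term. The SDs become sqrt(.1818 × .0316) = .076, sqrt(.1818 × .0568) = .102 and sqrt(.1818 × .0862) = .125. The ratios become 75%, 56% and 46%.

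**Simulation.** There were eight scenarios: ICC .05 or .10, true effect 0 or .29, and unmeasured dose confounding absent or present. Each had 40 data sets of 22 schools and 1225 students, with 250 placebo draws per data set.

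- Student-level placebo, ordinary regression: mean estimate about 0, SD .057 to .058, rejection 4.3% to 5.0% in all eight scenarios. Nothing changed when a true effect was present, or when confounding produced a dose slope of about .24 with no true dose effect.
- School-level placebo, ordinary regression ignoring schools: SD .11 to .16, rejection 30% to 48%. With no true effect, rejection was 30% to 33% at ICC .05 and 44% to 45% at ICC .10.
- School-level placebo, t-test on school means: rejection about 5%.

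BART itself was not simulated.

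**Precision of 250 draws.** For a 5% rate, the Monte Carlo standard error is sqrt(.05 × .95/250) = .014, with a 95% range of 2.4% to 8.0%.

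**The case against.** The strongest reply is that the paragraph is loosely written rather than wrong. It does not say that the draw is per student. It does say that the analysis bears on the BART models, so a refit may be intended. It nowhere commits the team to comparing the observed arm effect with the placebo spread. The BART targets are individual and dose-specific effects, for which a simple school contrast is not the exact null distribution. BART is also a supplementary, as-treated analysis; the primary HLM already carries random school intercepts and a leave-one-out sensitivity analysis.

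Much of this stands, and it rules out several stronger readings that a reader might infer:

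- **That the plan specifies an individual-level coin flip.** It does not. The student is the more natural unit, because a draw over 22 schools would correlate by chance with school covariates (SD about .2), which fits poorly with the stated lack of correlation. That remains an inference.
- **That the check will look reassuring whatever the truth.** This depends on the student-level reading. A school-level draw analysed without clustering rejects in 30% to 48% of draws, which would not reassure anyone.
- **That BART is definitely never run in the loop.** The documents support only that no refit is described.
- **That the primary intention-to-treat result is undermined.** It does not rest on this step.

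The reply does not rescue the stated purpose. Followed as written, on either unit, the step fits a regression of outcomes on a null variable and draws a conclusion about BART. Wanting a result to bear on BART is not a procedure that makes it do so.

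**Conclusion.** The concern holds in this form: the described step cannot support the claims about BART sensitivity or credible-interval robustness, and it has no pass criterion. That conclusion does not depend on the unit of the draw. Calling the variable an instrument is a mislabel.

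The size is conditional. It assumes a student-level draw, a placebo spread used as the noise benchmark, an unstratified 11 v 11 contrast with equal school sizes, and ICCs that the documents do not state. On those assumptions the spread is about 69%, 49% and 39% of the right size at ICCs of .02, .057 and .10.

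The matter is worth correcting because a better method is available and the present one would leave the robustness statement unsupported. It concerns the supplementary BART analyses.

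**What to change.** Replace the step with a permutation check:

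1. Re-draw school-to-arm assignment within site and randomisation stratum. The section on recruitment personnel says two schools were added in Year 3, one per condition, and describes no allocation rule for them. Treat them as their own pair and state that choice.
2. In each draw refit the same HLM (at least 1,000 draws) and the same BART model (as many draws as computing allows).
3. Compare the observed effect with that distribution, using a criterion written down before the analysis.
4. Remove the instrument wording.
5. Drop any claim that this check addresses the validity of the dose-response results, or add a separate sensitivity analysis for unmeasured confounding of dose. Permuting assignment does not test it.

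The cost is scripting and computing time, mainly for the BART refits. The permutation check needs no new data.
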